11. SPECIFIC AIMS

CTRC Review Complete

5/14/2015

[name]

COMIRB

APPROVED

19-Jun-2015

The growing T2D epidemic pose a major social and economic burden to society. Increasing physical activity associated with reduced CV morbidity and mortality in people with T2D. Physical activity levels are very low in people with T2D compared to similarly overweight nondiabetic people.¹ Thus, increasing physical activity in people with T2D remains a critical CV health priority. In prior RCTs of behavioral interventions in people with T2D,² physical activity levels increased in response to behavior change tools such as goal setting and motivational interviewing to overcome participant barriers. Integrating effective behavior change tools into clinical practice would provide a favorably broad reach. However, prior behavioral interventions were time and resource-intensive and such interventions may not be practical in **clinical practice settings**.² To move towards integrating physical activity interventions into clinical practice, we need behavioral interventions that are simple yet effective.^{3,4}

We have pilot data to suggest that trained clinical staff can successfully deliver a behavioral physical activity intervention. Also, our clinic and others⁵ have implemented valid methods that can identify sedentary patients who could benefit from treatment. In this grant application, we propose an innovative approach that fully integrates both trial recruitment standards (i.e., assessing participant inclusion/exclusion criteria) and intervention delivery methods into clinical practice settings. The chief advantages of the proposed work are: 1) using clinical staff and clinical processes to include appropriate patients who may be safely active — true clinical integration; 2) adding reimbursable in-person treatment visits with a physician assistant who coordinates treatment with clinic health promotion counselors — enhances safety and improves translational potential.

My K23 research objective is to pilot-test the feasibility and effectiveness of an evidence-based physical activity counseling intervention that is tailored to patient barriers and facilitators. My rationale is that the proposed research could shift the paradigm of physical activity counseling in primary care by developing an intervention that utilizes evidence-based behavior change methods but is brief enough to be widely implemented in clinical practice. We are powered to detect differences in physical activity and we also expect improvement in our secondary outcomes related to physical activity and physical function.

My focus previously was on lab-based supervised exercise to increase physical activity in adults with T2D and normal physical function — this has evolved to focus on translational research in primary care to increase physical activity in adults with T2D who often have physical function limitations. Therefore, my K23 training goals are to acquire advanced skills in: 1) functional assessments and rehabilitation of adults with functional limitations and 2) implementation science methods. Meeting my K23 goals for training and research will position me to lead the way to develop, test and implement clinical treatments to improve health and function for adults with T2D who are at high risk of cardiovascular disease.

Purpose: Conduct a randomized controlled trial with 1:1 patient-level randomization to an evidence-based physical activity program intervention vs. usual care in sedentary adults with T2D (n=130) in 2 primary care clinic sites to test two aims.

Aim 1: Determine the effectiveness of a 12 week evidence-based physical activity program delivered by designated clinical staff and physician assistants, as compared to usual care, on:

1a) physical activity by accelerometer (primary outcome) and physical activity predictor outcomes from the social cognitive theory (SCT) of behavior – e.g., self-efficacy, social-environmental support

1b) physical function by physical performance measures (secondary outcome) and the physical function predictor of lower extremity strength

Hypothesis 1: Objective physical activity and physical function will increase more in the intervention vs. usual care study group.

Aim 2: Assess process measures among patients, clinical staff, clinical providers, and practice leadership to determine acceptability and time burden.

Hypothesis 2a: Over 80% of intervention patients would recommend the intervention to a friend.

Hypothesis 2b: Over 80% of clinical staff/providers would recommend continuing to offer the intervention.

Impact: By determining the effectiveness of this program and by filling my training gaps, this K23 proposal has great translational potential to improve the health of adults with T2D. It also prepares me to be a national leader in the implementation of evidence-based physical activity programs at other clinical sites.

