12.3 APPROACH

12.3a. OVERALL RCT STUDY DESIGN The overarching goal of this proposed research is to determine whether an evidence-based intervention that is reimbursable in U.S. clinics will improve physical activity and physical function. To our knowledge, no studies have fully integrated these research programs into clinical practice. Thus, we designed this study to determine the effectiveness (Aim 1) and acceptability/time burden (Aim 2) of integrating an intervention for adults with T2D. For Aims 1-2, we will assess outcome measures at time = 0 (baseline) and time = 3 months (post-intervention). We provide a detailed timeline for our proposed research procedures (Table 5) to complement the timeline of training and career development activities in section 4. (Career Development Plan)

Table 5. K23 project timeline

	Year											
	Quarter				Year 2 – 2016				Year 3 – 2017			
Quarter	1	2	3	4	1	2	3	4	1	2	3	4
Project Phase												
Adaptation of screening and intervention for primary care	x	x										
Pilot-test intervention		x										
Patient recruitment and Screening		x	x	x	x	x	x	x	x	x	x	
Randomization of patients to intervention or usual care with accumulated participant goal (n) per quarter		5	20	35	50	65	80	100	115	130		
Data analyses of primary and secondary outcomes (Aim 1)											x	x
Process measure evaluation in participants and clinic system (Aim 2)			x	x	x	x	x	x	x	x	x	
K23 milestones: future grant submissions and manuscripts. See Table 3 timeline in “Career Development plan”		A			B		R01			R01		C

12.3b. ADAPTATION OF THE SCREENING ALGORITHM AND INTERVENTION FOR PRIMARY CARE

Because we are adapting the pilot CU LIFE intervention that is currently coordinated by research staff, we will need a pre-RCT adaptation phase to fully integrate the study procedures into the clinic. In this adaptation phase, the PI will meet monthly with an expert advisory team representing K23 mentors in physical activity in T2D ([name]), endocrinology ([name]), physical therapy ([name]), physical activity behavior counseling ([name]), health promotion clinic staff who will deliver the counseling, and clinic physician assistants who will conduct the screening and monitor the treatment.

Clinical screening algorithm (Table 6): First, we will optimize the clinical screening algorithm in consultation with our expert advisory team. Next, in months 4-6, the PI will train four clinic physician assistants (n = 2 from

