Overcome barriers: Rather than suggesting solutions, counselor invites participant to solve the barriers to activity he/she identified. Counselor adds advice on time management strategies.
Tracking: Participant records daily type and times of activity K23 Optimization: Wearable device simplifies ability to track activity

consent, participants will undergo 1:1 patient-level randomization to the intervention or usual care group. (Figure 5)

Study Settings: Enrollment (V1), Baseline testing (V2-3), and Exit testing (V10-11) will be conducted in the CCTSI outpatient Clinical Translational Research Center.

12.3f. INTERVENTION GROUP

Figure 5. [name] NIDDK K23 Study Flow

The proposed intervention is based on SCT (Figure 4 in “Significance”) and seeks to increase physical activity and improve strength by addressing individual, behavioral, and social/environmental factors. The health promotion clinic staff will deliver counseling by phone on a bi-weekly basis — a clinic physician assistant will coordinate with the counselor during in-person clinic visits (Figure 3 and Table 8), teach participants to perform strengthening exercises; and assess for safety concerns, such as hypoglycemia. We optimized the existing VA LIFE intervention in our funded CU LIFE pilot, by simplifying the VA LIFE counseling guide for delivery as brief, tailored counseling by health promotion clinic staff (see Appendix), and by adding strengthening exercises that engage multiple muscles (see Appendix). To ensure the intervention is brief enough for clinical use and to incorporate T2D-specific barriers and facilitators, we will make further adaptations in the pre-RCT Adaptation phase, as described above in 12.3b.

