Hypothesis 1. Using intent to treat principles, we will test for differences between the intervention and usual care groups on physical activity at the 3 month assessment. We will assess the intervention effect size of change in physical activity from baseline testing to 3 months using an ANCOVA model with adjustment for age; covariates from Table 10 (e.g., cognitive processing speed); and each participant's baseline score. Adjustment for baseline score is useful in this relatively small RCT to eliminate any potential baseline differences between groups that may occur despite the randomization procedure. We expect that the mean physical activity at 3 months will be significantly higher in the intervention group than in the usual care control group. Every attempt will be made to ensure high retention rates at posttest, although some attrition is to be expected. The level and patterns of missing data will be evaluated relative to intervention condition and other baseline characteristics to determine whether there is systematic bias in the missing data. If necessary and appropriate, based on the level and patterns of missing data, state-of-the-art techniques (e.g., multiple imputation) will be used.

Aim 1 secondary outcomes. The analyses for Aim 1 secondary outcomes will be used to detect trends and to provide necessary data to calculate the sample size needed to detect differences in a larger RCT. We will assess the intervention effect size by calculating a Cohen's d effect size comparing the means of the two groups at the three-month follow-up. We will use separate ANCOVA models to assess pre-post intervention changes in the following outcomes listed in Table 10: physical function by 400-meter rapid gait speed (differentiates adults with higher baseline function); Short Physical Performance Battery (differentiates adults with lower baseline function); intermediate physical activity behavioral constructs from SCT; intermediate functional outcome (lower extremity strength); and metabolic outcome (Hemoglobin A1c).

Table 10. Outcome, Predictor, and Covariate Measures for [name] K23

Outcome	Instrument	Variable	Measure
Physical Activity outcomes			

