Physical function	The Short Physical Performance Battery (SPPB) measures function with the following valid subscales: balance, usual walking speed, and repeated chair rise. The SPPB is sensitive to change for adults with moderate to severe functional impairment , and predicts disability and mortality. ^{68,89}	Ordinal, range 0-12	Aim 1 2° outcome
Lower extremity strength	Lower extremity strength will be measured as leg extensor (quadriceps) and leg flexor (hamstring) strength using [name] laboratory's established techniques. ^{38,90}	Continuous	Aim 1 Function predictor
Grip strength	Hand grip strength will be measured by dynamometer. ⁹¹	Continuous	Aim 1 2° outcome
Metabolic control outcome			
Hemoglobin A1c	Average glycemic control measured by standard methods ⁹²	Continuous	Aim 1
Covariates for adjustment			
Depression symptoms	Center for Epidemiologic Studies Depression Scale measures depressive affect severity and is valid in people with ^{93,94} and without T2D. ^{95,96}	Continuous	Aim 1 covariate for adjustment
Lower extremity arthritis pain symptoms	Western Ontario and McMaster Universities Arthritis Index—valid measure of knee and hip pain and stiffness. ⁹⁷	Continuous	Aim 1 covariate
Cognitive processing speed	Stroop test –measures cognitive processing speed as a valid predictor of cognitive function in adults with and without T2D. ⁹⁸⁻¹⁰⁰	Continuous	Aim 1 covariate

DEXA scan	DEXA will allow the calculation of body composition as fat-free mass and total mass so that we may report exercise performance levels standardized to these body composition measures.	Continuous	VO ₂ max covariate for adjustment
Cognitive executive function	Behavioral Dyscontrol Scale – valid measure of executive function in adults with and without T2D. ^{101,102}	Continuous	Aim 1 covariate
Process outcomes			
Acceptability	Percent of intervention patients who would recommend intervention ¹⁰³ ; Percent of clinical providers/staff who recommend continuing to offer the intervention to patients ¹⁰³	Percentile	Aim 2
Time burden	Patient time required for each intervention visit ¹⁰³ ; Staff/provider time required for each intervention visit ¹⁰³	Continuous	Aim 2
Safety outcomes			
	Participant report of outcomes after baseline testing: falls, musculoskeletal injuries, foot ulcers, hypoglycemia ^{20,24,57}	Continuous	Safety

12.3k. ANALYSIS OF ACCEPTABILITY OUTCOMES (Aim 2 and Safety analysis)

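### Clinic is a known design factor in this two-clinic trial, but no stratification by clinic is described and clinic is not an ANCOVA term: a small, nearly free gain in balance and precision is left unused

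*Combined protocol and SAP*

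**What the plan says.** Section 11 (Purpose) places the trial "in 2 primary care clinic sites to test two aims". Section 12.3e gives the allocation: "participants will undergo 1:1 patient-level randomization to the intervention or usual care group". The text mentions no stratification factor, blocking or method of generating the sequence.

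Section 12.3b states that "the PI will train four clinic physician assistants", two from each clinic, and describes them as "clinic physician assistants who will conduct the screening and monitor the treatment". Under sections 12.3d and 12.3f they apply the exclusion criteria at the screening visit, teach the strength exercises and check safety at the in-person visits.

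Section 12.3j (Hypothesis 1) sets the primary model: "using an ANCOVA model with adjustment for age; covariates from Table 10 (e.g., cognitive processing speed); and each participant's baseline score". The block of Table 10 headed "Covariates for adjustment" lists depression symptoms, lower-extremity arthritis pain, cognitive processing speed, DEXA (for VO2max) and executive function. Clinic is not in it.

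For Aim 1 secondary outcomes, section 12.3j plans separate ANCOVA models and also a Cohen's d from the two groups' means at three months. No adjustment is described for that d, which is meant to help size a later trial.

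**The concern.** Clinic is known for every patient before randomization and determines which physician assistants screen that patient. If activity or function differs between the clinics, an allocation that ignores clinic can by chance put more of one clinic's patients in one arm. Part of the clinic difference then moves the treatment estimate, and a model without clinic leaves the clinic variation in the error term. The plan already accepts this reasoning for the baseline score: it adjusts because the trial is fairly small and chance differences can survive randomization. At stake is some precision in the primary comparison and the cleanness of the secondary effect sizes that a larger trial would rely on.

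**Working it through.** **Inputs from the documents (12.3j):** d = 0.61, two-sided alpha 0.05, 90 evaluable (45 per arm), 130 enrolled, up to 30% attrition.

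**Assumptions, because the documents give no figures:** clinic split 50:50 (30:70 as a check); equal arms without stratification; a clinic gap in SD units; a baseline-to-exit correlation r.

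**1. The plan's own figure.** Noncentrality = 0.61 × √(45/2) = 2.89. Power is 81.6% by noncentral t with 88 df (82.5% by the normal approximation), which agrees with the stated figure of over 80%. For attrition, 90/0.7 = 128.6, so 129 against the 130 planned. Neither figure is in question.

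**2. Chance imbalance.** With equal arms, the number of clinic-A patients in one arm is hypergeometric.
- N=130: variance = 65 × 0.25 × 65/129 = 8.19, SD 2.86. The difference in clinic share between arms has SD 2 × 2.86/65 = 8.8 points. P(10 points or more) = 29%; P(20 or more) = 3%.
- N=90: variance = 45 × 0.25 × 45/89 = 5.69, SD 2.39, so 2 × 2.39/45 = 10.6 points. P(10 or more) = 40%; P(20 or more) = 9%.
- With a 30:70 split, P(10 or more) is 25% at N=130 and 36% at N=90.

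**3. Shift in the primary estimate.** Shift = imbalance × clinic gap left after baseline adjustment. For a stable gap of 0.5 SD, what remains is 0.5 × (1 − r).
- r = 0.5: 0.25 SD remains. A 10-point imbalance shifts the estimate by 0.025 SD; 0.025/0.61 = 4%.
- r = 0.7: 0.15 SD remains. The shift is 0.015 SD; 0.015/0.61 = 2.5%.

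The unadjusted standard error at N=90 is √(2/45) = 0.211 SD. Multiplied by √(1 − r²), it becomes 0.183 (r = 0.5) or 0.151 (r = 0.7). These shifts are therefore about 10 to 14% of one standard error.

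**4. Residual variance explained by clinic** (50:50 split): 0.25 × (remaining gap)² / (1 − r²).
- r = 0.5: 0.25 × 0.0625/0.75 = 2.1%.
- r = 0.7: 0.25 × 0.0225/0.51 = 1.1%.

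**5. Power with clinic in the model** (N=90, 87 df). Residual variance is multiplied by 1 − q(1 − q) × gap², where q is the clinic share and the gap is the remaining clinic difference in residual SD units.

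| Remaining gap (SD) | Power, 50:50 | Power, 30:70 |
|---|---|---|
| 0 | 81.6% | 81.6% |
| 0.1 | 81.7% | 81.7% |
| 0.2 | 82.0% | 82.0% |
| 0.3 | 82.5% | 82.4% |
| 0.5 | 84.0% | 83.6% |

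The gaps in step 3 are 0.25/√0.75 = 0.29 and 0.15/√0.51 = 0.21 on this scale, so the gain is under 1 point. If clinic has no effect, the lost degree of freedom costs about 0.01 points.

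**6. Secondary Cohen's d.** No baseline term is described, so the whole gap counts. A 10-point imbalance shifts d by 0.03 at a 0.3 SD gap and 0.05 at 0.5 SD; a 20-point imbalance shifts it by 0.06 and 0.10.

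**7. What stratification leaves after attrition.** With clinic balanced at randomization and 20 of 65 lost at random in each arm, the clinic share in one arm has variance 0.25 × (20/64)/45 = 0.00174. The between-arm difference has SD √(2 × 0.00174) = 5.9 points, against 10.6 without stratification.

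**The case against.** The documents give good reasons to expect a small clinic effect. Both clinics are internal medicine practices of one university, searched with one electronic query (12.3c). Baseline and exit testing take place in one research unit (12.3e), so there is no site effect on measurement. Counseling comes by phone from off-site staff (Figure 3). All four assistants are trained on one screening algorithm to a kappa of at least 0.81 (12.3b). In-person visits during treatment occur only in the intervention arm (Table 8), so differences in how assistants run them would mainly make the effect vary by clinic, which a clinic main effect does not model. All of this stands, and it is why the gain is modest. It does not rule out differences in patient mix or in who passes screening.

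A reader might go further in three ways that the documents do not support.
- *That allocation is unstratified.* The text is silent on the method, and the study-flow figure (Figure 5) and appendices were not available for this check. Only the absence of a description can be claimed. The missing model term does not depend on this, because the terms are listed.
- *That the full clinic difference enters the primary estimate.* A raw 0.5 SD gap would give a 0.05 SD shift (8% of 0.61) and about 6% of variance, but only without baseline adjustment, which the primary model includes.
- *That the result is biased or the power wrong.* Chance imbalance under patient-level randomization is not systematic bias; the unadjusted standard error and type I error already allow for it.

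Blocked lists within clinics can also make allocation easier to guess in an unblinded behavioral trial. That is a fair caution, and the fix has to deal with it.

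**Conclusion.** The point holds as a minor improvement in balance and precision. Clinic is missing from the described allocation and from the listed model terms, and including it costs almost nothing. For the primary outcome the expected benefit is a few percent of the planned effect at a 10-point imbalance, and less than 1 point of power for remaining clinic differences up to 0.3 SD. The benefit of stratification is largest for the unadjusted secondary Cohen's d. The sample size needs no change. The sizes rest on an assumed clinic split, clinic gap and baseline-to-exit correlation, and the N=90 figures also assume that losses are unrelated to clinic and arm.

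**What to change.** 1. State the allocation method in 12.3e and stratify the 1:1 allocation by clinic: one list per clinic, with varying block sizes and concealed from the staff who enroll.
2. Prespecify clinic as a fixed factor in the Aim 1 ANCOVA models in 12.3j. This also deals with imbalance that arises through attrition after a stratified start.
3. If randomization has already started, add the model term alone and fix it before the outcome data are analyzed. The unadjusted secondary d then stays exposed and should be read beside the ANCOVA result.

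Cost: two lists instead of one, some care with concealment, and one degree of freedom. No extra patients, visits or data are needed.

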12. RESEARCH STRATEGY

12.1 SIGNIFICANCE

12.1.1. Ongoing Importance of physical activity for CV disease prevention in T2D The prevalence of diabetes mellitus has more than tripled in the past 30 years, and currently affects 25.8 million Americans.⁶ T2D accounts for >90% of prevalent diabetes cases in adults.⁷ Because people with T2D are at very high risk for CV disease, people with T2D are a high priority NHLBI study population.⁸⁻¹¹ Several large observational studies support regular physical activity as a potent therapy to reduce CV mortality in people with T2D.¹²⁻¹⁵ A recent meta-analysis of prospective cohort studies found improved CV outcomes in participants with diabetes by physical activity strata (HR = 0.61 (0.47-0.80) for CV mortality for highest vs. lowest physical activity levels).¹⁶ Data from RCTs have been mixed, as lower stroke event rates (HR = 0.62 (0.35-0.98) were observed in the intervention vs. placebo group of an RCT of a behavioral intervention that increased physical activity¹⁷, but the Look AHEAD study was stopped for lack of group differences in CV outcomes¹⁸. Lower than expected CV outcomes in both Look AHEAD

study groups may have under-powered this study to detect an intervention effect.¹⁸

[figure not shown]
Overall, the consistent benefits of regular physical activity with regard to cardiorespiratory fitness, CV mortality, and all-cause mortality that have been observed in large cohort studies provide a convincing evidence base that regular physical activity improves CV health. Also, one study found mean annual health costs were ~\$2000 less in people with T2D who performed physical activity ≥ 2 times/week vs. <1 time/week.¹⁹ Thus, regular physical activity, a critical cornerstone of T2D treatment, may actually generate cost savings.²⁰

12.1.2. Why improve function? PFLs predict disability, loss of independence, and premature mortality for adults.²¹⁻²³ Regular physical activity can preserve function and reduce these adverse outcomes.²⁴⁻²⁷

12.1.3 Why develop a treatment specifically for adults with T2D? Adults with T2D develop worse physical function at an earlier age than their nondiabetic peers,^{22,28} and regular physical activity is one of the only effective interventions.^{24-27,29} Adults with T2D may develop premature PFLs due to specific factors associated with T2D^{8,22,30-40} (Figure 2). Physical activity programs for adults with T2D and PFLs need to assess participants' balance, cognition, and symptoms during ambulation in order to avoid enrolling participants who are unsafe to perform physical activity independently.^{24,41} Because regular physical activity improves

Abbreviations: Type 2 Diabetes (T2D); Physical function limitations (PFLs); Patient-centered Medical Home (PCMH); Social Cognitive Theory (SCT)

Figure 2. Pathophysiology* of Physical Function Abnormalities in T2D

*Adapted from conceptual model by Nocera and Pahor et al., J Aging Research, 2011

Figure 3. Activities during in-person vs. phone visits during intervention

Phone intervention visits
Point of contact: Telephone call
Clinic involvement:

 Health promotion clinic staff: 
 Brief counseling Tailored to unique individual barriers/benefits from baseline surveys Recommend short bouts of activity on most days On individual basis, gradually ↑activity goals and strength exercise goals towards U.S. physical activity guidelines If clinical concerns arise, can call clinic nurse or physician assistant Schedules next intervention visit

In-person intervention visits
Point of contact: Visit in primary care clinic with physician assistant
Clinic involvement:

 Usual vital signs and check-in Physician assistant: 
 Monitors intervention safety Ensures proper form for strength exercises Telephone handoff to health promotion clinic staff Health promotion clinic staff: 
 Phone counseling from off-site allows continuity of counselor throughout the intervention Identical counseling content to phone intervention visit Schedules next intervention visit

glycemic control.⁴²⁻⁴⁴ treatment programs for adults with T2D should also monitor for glucose trends during the program and adjust medication doses as needed to avoid hypoglycemia. Existing physical activity programs have not always included these important safeguards — in part, because they were not integrated into clinics.²⁴ The proposed K23 trial will include these screening and treatment monitoring safeguards.

12.1.4 Why should we deliver an intervention in clinical practices? There are several reasons why clinical care settings are a highly relevant way to deliver interventions to treat adults with T2D and sedentary behavior. Clinical practices have key implementation features of **capability, motivation, and opportunity**.^{45,46} Despite these features, primary care clinics do not deliver evidence-based counseling programs due to several concerns, such as: excessive staff and clinician burden, lack of reimbursement, and lack of training for clinicians/staff to deliver counseling.⁴⁷⁻⁴⁹ To integrate an activity intervention in clinics, we need to develop programs that address these barriers in a way that may be replicated in other systems.

[figure not shown]
One way to address these barriers is developing at the national level. Primary care clinics have evolved dramatically over the past decade to better identify certain patient populations at high risk for disease — and proactively treat them. This model of care is termed the patient-centered medical home (PCMH), and its prevalence is growing rapidly.^{50,51} An important PCMH characteristic is to use teams to manage patients' health. For example, PCMHs employ special health promotion clinic staff who call patients to address specific health targets (e.g., schedule routine diabetes visits, provide simple lifestyle counseling).⁵²⁻⁵⁴ Using teams offers lower cost alternatives to treat sedentary adults with T2D: it costs less for health promotion clinic staff to deliver counseling compared to clinicians; also, clinicians can remain engaged to see patients in clinic to monitor treatment — a unique **capability** that we leverage in the proposed K23 (Figure 3). If effective, this K23 treatment model could be implemented in other PCMH clinics nationally. Clinics that are not PCMHs could also feasibly adapt this model and designate a clinician to deliver the counseling — but greater costs to the clinic and excessive clinician burden make the proposed K23 approach more optimal. The **motivation** for clinic leadership to deliver interventions is to improve quality of life and preserve functional independence for patients. The **opportunity** is to deliver a relatively simple yet impactful intervention in a way that provides repeated counseling to patients — regular and repeated counseling is important to change behavior.⁵⁵⁻⁵⁹ Another opportunity is to deliver this treatment in a way that overcomes a translational barrier — reimbursement for in-person visits. Payers will likely be interested in this type of program due to the potential to prevent costly falls in adults with T2D and PFLs.²⁹

